7.3 Lost to Follow-up

A participant will be considered lost to follow-up if the participant repeatedly fails to return for scheduled visits and is unable to be contacted by the study site.

The following actions must be taken if a participant fails to return to the clinic for a required study visit:

- The site must attempt to contact the participant and reschedule the missed visit as soon as possible and counsel the participant on the importance of maintaining the assigned visit schedule and ascertain whether or not the participant wishes to and/or should continue in the study.

- Before a participant is deemed lost to follow-up, the investigator or designee must make every effort to regain contact with the participant (where possible, 3 telephone calls and, if necessary, a certified letter to the participant's last known mailing address or local equivalent methods). These contact attempts should be documented in the participant's medical record.
- Should the participant continue to be unreachable, she will be considered to have withdrawn from the study.

Discontinuation of specific sites or of the study as a whole are addressed in [Section 10.1](#) ([Appendix 1](#)).

7.4 Non-interventional (Observational) Sub-study – Subject Decision to Withdraw

Participants have the right to withdraw from the study at any time and for any reason without prejudice to their future medical care by the physician or at the institution. Withdrawal of consent for a study means that the participant does not wish to or is unable to continue further study participation. Participant data up to withdrawal of consent will be included in the analysis of the study and, where permitted, publicly available data can be included after withdrawal of consent. The investigator is to discuss with the subject appropriate steps for withdrawal of their consent from the study.

8 STUDY ASSESSMENTS AND PROCEDURES

Interventional study procedures and their timing are summarized in the SoA ([Section 1.3](#), [Table 1-3](#)). Non-interventional (observational) sub-study procedures and their timing are summarized in the SoA ([Section 1.3](#), [Table 1-4](#)). Protocol waivers or exemptions are not allowed.

Immediate safety concerns should be discussed with the Sponsor immediately upon occurrence or awareness to determine if the participant should continue or discontinue study intervention.

Adherence to the study design requirements, including those specified in the SoA ([Section 1.3](#)), is essential and required for integrity of study conduct.

Information on how samples are to be stored, processed, and shipped is provided in the Laboratory Manual.

8.1 FNAIT Laboratory Screening Assessments

In participants presenting at GW 6 or after who provide informed consent, blood samples will be collected at the Screening Part 1 visit to assess for higher risk for the occurrence of HPA-1a alloimmunization and FNAIT during their pregnancy.

The first test will be a test for maternal HPA-1 genotype. In participants identified as HPA-1b/b (ie, HPA-1a negative), subsequent tests will be performed to confirm the participant has an HLA-DRB3*01:01 positive genotype, is anti-HPA-1a alloantibody negative, and is carrying an HPA-1a/b (ie, HPA-1a positive) fetus.

8.1.1 *Screening Part 1*

The screening test paradigm is provided in [Table 8-1](#).

Table 8-1 Screening Test Paradigm

Test No.	Test	Description		Result	Screening Specific Action
1	Maternal HPA-1 genotype	Test will identify women who are HPA-1b/b, indicating risk for HPA-1a sensitization and occurrence of FNAIT	1a	HPA-1b/b (HPA-1a negative)	Perform Test 2 and 3
			1b	HPA-1a/b; HPA-1a/a	None – no further testing (ineligible)
2	Maternal HLA-DRB3*01:01 genotype ^δ	Test will identify women who are HLA-DRB3*01:01 positive, indicating a higher alloimmunization risk; performed concurrently with Test 3	2/3a	HLA-DRB3*01:01 positive, Anti-HPA-1a antibody negative	Perform Test 4
3	Maternal anti-HPA-1a antibody ^δ	Test will establish women who have no detectable anti-HPA-1a antibody; performed concurrently with Test 2	2/3b	HLA-DRB3*01:01 positive, Anti-HPA-1a antibody positive	None – no further testing (ineligible)
			2/3c	HLA-DRB3*01:01 negative, Anti-HPA-1a antibody negative	None – no further testing (ineligible)
4	Fetal HPA-1 genotype	AcffDNA test to inform on the presence of the antigenic stimulus for maternal alloimmunization	4a	HPA-1a/b	Treat with SC RLYB212 and follow up for final assessments
			4b	HPA-1b/b	None – no further testing (ineligible)

cffDNA = cell-free fetal DNA; FNAIT = fetal and neonatal alloimmune thrombocytopenia; HPA = human platelet antigen

^δ Note: for operational efficiency, Test 2 and Test 3 are performed simultaneously

Screening Part 1 is an initial visit that includes the informed consent, demographic questioning (including obstetric history), and the collection of a blood sample for FNAIT testing (Table 1-2). This visit is to take place no earlier than GW 6. Individuals will consent to HPA-1 genotyping (Test 1) and, if HPA-1b/b, subsequent screening for HLA-DRB3*01:01 (Test 2), anti-HPA-1a antibodies (Test 3), and confirmation of fetal HPA-1a genotype (Test 4), as required.

Two distinct samples and analyses are performed, per industry practice, to confirm absence of the HPA-1b allele in the fetus, with timing between sampling ~2 weeks.

8.1.2 Screening Part 2

Participants who meet all eligibility criteria in Screening Part 1 (SoA, Table 1-3, ie, HPA-1b/b and HLA-DRB3*01:01 positive genotype; anti-HPA-1a alloantibody negative; fetal HPA-1a/b genotype) and who provide informed consent for Screening Part 2 (SoA, Table 1-3) will be assessed to determine if they meet all eligibility criteria to enter the antenatal treatment phase and to receive treatment with RLYB212 according to the protocol.

Dosing with RLYB212 will be initiated at Visit 3, which must occur no later than GW 16. That is, if the fetal HPA-1 genotype is pending and will not be available by the planned baseline visit at GW 16, the subject will be dosed with the initial dose of RLYB212 pending the result (of the

replicate tests), provided all other Screening Part 2 criteria are met. A second dose of RLYB212 will not be given if definitive fetal HPA-1a results are not available by Visit 4 (~GW 20). If the fetal HPA-1a genotype data become available after the initial dose of RLYB212 is given and the fetus is HPA-1b/b, ie, not at risk for HPA-1a alloimmunization, the participant will be discontinued from treatment, followed at a safety visit 4 weeks later and then discharged from the study to receive normal prenatal care and follow-up by their physician. In this case, the participant would have been determined not to be at risk for development of HPA-1a alloimmunization and FNAIT.

The study has been designed with multiple sequential cohorts ([Section 1.2.1](#)). Therefore, if a participant has been determined to be eligible for RLYB212, but the cohort has been fully enrolled, the participant will be requested to consent for the non-interventional (observational) sub-study.

Eligibility for the non-interventional (observational) sub-study is presented in [Table 1-1](#).

8.2 Pharmacokinetic Assessments

Serum samples will be collected for measurement of concentrations of study drug as specified in the SoA ([Section 1.3](#)).

The timing of sampling may be altered during the study based on emergent data (eg, to obtain data closer to the time of peak serum concentrations) to ensure appropriate monitoring.

A cord blood sample will be collected at parturition to inform neonate exposure to RLYB212.

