
To assess maternal and fetal safety of RLYB212 during pregnancy	
Type, seriousness, and incidence of AEsPhysical examination findingsVital signsMaternal clinical laboratory valuesECGObstetric/fetal doppler ultrasound
Secondary	

To evaluate RLYB212 exposure in the neonate at delivery	
Concentration of RLYB212 in cord blood

To assess the safety of RLYB212 in the HPA-1a positive neonate	
Type, seriousness, and incidence of AEs including fetal/neonatal AEsPhysical examination findings, including APGAR scoresVital signs

To assess the immunogenicity of RLYB212	
Development of ADAs

To assess pregnancy and neonatal outcomes following antenatal RLYB212 administration	
Number of spontaneous abortionsNumber of elective abortionsNumber of stillbirthsNumber of premature birthsNumber of full term births (≥ 37 completed weeks of gestation)Overall health and development of infants at 4-6 weeks and 12 months of age

To assess the occurrence of neonatal thrombocytopenia following antenatal RLYB212 administration	
Neonatal thrombocytopenia^a and severe neonatal thrombocytopenia

To assess the occurrence of HPA-1a alloimmunization	
Presence of maternal anti-HPA-1a alloantibodies at Week 10 post pregnancy^b

ADA = anti-drug antibody; AE = adverse event; APGAR = Appearance, Pulse, Grimace, Activity, and Respiration; ECG = electrocardiogram; HPA-1a = human platelet antigen 1a; PK = pharmacokinetic(s); SC = subcutaneous.

^a Evaluation of neonatal thrombocytopenia will be based on the umbilical cord sample taken at parturition.

^b For pregnancies that do not result in a live birth, the assessment of alloimmunization will be at 10 weeks from the date of the pregnancy-terminating event (ie, abortion [spontaneous/elective] or stillbirth).

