A second 4-week repeat-dose GLP toxicity study of SC administration was conducted to evaluate the potential toxicity, the TK properties, and the potential reversibility of RLYB212 in heterozygous antigen positive mice. Groups of male and female heterozygous APLDQ mice received RLYB212 SC injections at 0.025 mg/kg once weekly. It is noted that the assay used to measure RLYB212 in circulation detects only free drug, which limits the ability to accurately assess exposure levels in antigen positive animals; therefore, a parallel TK control arm in WT mice was included for estimation of RLYB212 exposures. RLYB212 was well tolerated with average C_{max} exposure margins up to 12.5-fold over the target upper boundary in IPA2202 after the first dose and 47-fold over the target upper boundary after the last dose, with no drug-related clinical signs or effects on body weights or body weight gains. Observed effects on hematology in both antigen positive and negative animals (increase in lymphocytes, neutrophils, and total white blood cells) were considered non-adverse and were reversible.

Reproductive toxicology studies were conducted in female WT mice bred to transgenic APLDQ sires, to mimic the population of HPA-1b/b women bearing an HPA-1a positive fetus. Parallel control dose groups in pregnant mice bearing antigen-negative litters were utilized to confirm the relative ratio of maternal to fetal/neonatal exposures after dosing with RLYB212 during gestation and lactation. An additional study was also conducted in pregnant mice bearing antigen-positive litters to evaluate histopathology of heterozygous HPA-1a antigen-positive fetal-derived tissues (placenta, fetus, and neonate).

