Over the series of reproductive toxicology studies that were performed, RLYB212 did not cause any adverse effects on mice during reproduction or embryo-fetal developmental (EFD) studies, ie, there were no effects on gestation, parturition, lactation, or maternal behavior in the dams and no effects on mortality, growth, or sexual maturation in their offspring. Minimal findings were noted from one study only, which included slightly increased post-implantation losses and slightly decreased fetal bodyweights in the 0.125 mg/kg dose group. Post-implantation losses in this study were variable and included several individual dams across all dose groups with losses which exceeded twice the standard deviation. Individual animal data included one dam each in the control and low dose group which were excluded due to early delivery. Decrease in fetal bodyweight was mild in the high dose group. While anti-drug antibodies (ADAs) were not measured in this study, immunogenicity could be related to these findings as RLYB212 concentrations varied and were undetectable in several animals.

This evaluation, taken together with the overall developmental and reproductive toxicity (DART) package including four other studies where no increase in post-implantation losses or decrease in pup fetal bodyweight was noted, led to an overall assessment of low risk for reproductive toxicity. Exposure margins from the reproductive toxicity package of studies ranged from average C_{max} margins in pregnant dams of up to 65-fold at gestation day 18 and 242-fold at lactation day 5. While direct measurement of RLYB212 exposure in heterozygous antigen positive offspring was not possible, antigen negative control groups demonstrated RLYB212 fetal exposures in utero at gestation day 18 of ~1-3 fold greater than those measured in the dams. Extrapolation of maternal:fetal/neonatal exposure ratios in control groups in combination with direct measurement of RLYB212 in antigen negative dams bearing antigen positive offspring enable projected exposure margins in antigen positive fetuses and neonates well over 10-fold greater than the target upper boundary of ~10 ng/mL in IPA2202. A tissue cross reactivity (TCR) study was conducted consisting of a panel of 37 adult human tissues; RLYB212 staining to the

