	
Cell-free fetal DNA collected for fetal genotyping is at low levels before GW 10 (<3% of total maternal circulating cfDNA and gradually increases by about 1% by Week 20). [15] Due to these low levels of fetal DNA prior to GW 16, confirmation of fetal HPA-1 genotype may come after initial dose of RLYB212 at GW 16. (Section 8.1.1 and Section 8.1.2). Consequently, some participants carrying a potentially HPA-1b/b fetus will be exposed to the loading dose of RLYB212 despite not being at risk for alloimmunization.	
The Phase 2 study (IPA2202) employs sentinel subject dosing through pregnancy followed by two sequential, sequenced cohorts. Modification of the RLYB212 dose regimen may be performed during the study based on available PK data from participant(s) with a completed pregnancy, to ensure desired steady state concentrations are maintained through pregnancy and parturition between a target lower bound of ~3 ng/mL and a target upper bound of ~10 ng/mL.For women receiving RLYB212 loading dose (0.12 mg) before the fetal genotype is definitively determined, there is a ~85% chance that the fetus will be HPA-1a/b and hence express the antigen (due to the prevalence of the HPA-1b gene and application of the Hardy-Weinberg principle in the case of unknown paternal genotype). In that case, all aspects to mitigate fetal/placental harm noted above will be in place and the loading dose will have been administered appropriately. There remains a roughly 15% chance, however, that the fetus will be determined to be HPA-1b/b, consistent with the maternal genotype. In this case, RLYB212 administration will be stopped, and the pregnancy will be followed for an additional 4 weeks for safety and PK assessment. Since RLYB212 is directed against the HPA-1a epitope, which neither mother nor fetus express, the antibody will not bind to maternal or fetal tissues. Therefore, RLYB212 is expected to pose no risk other than that of any exogenous monoclonal antibody, as outlined under “Maternal Risks” within this table.Fetal doppler ultrasound monitoring will be performed at regular intervals during the study and consistent with obstetric standard of care, to detect any evidence of placental structural abnormality, organ pathology, hemorrhage, or delayed growth in the fetus.A cord blood sample will be collected at delivery to evaluate fetal exposure to RLYB212.

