9.4.3 Secondary Endpoints

RLYB212 exposure in the neonate will be evaluated by cord blood concentration of RLYB212, which will be a single measurement, and neonatal thrombocytopenia will likewise be evaluated by cord blood platelets.

Other aspects of safety of RLYB212 exposure in the neonate will be evaluated during the postpartum follow-up period in terms of type and seriousness and incidence of AEs, physical examination findings including APGAR scores, vital signs and cord blood levels for platelets, hematocrit, hemoglobin, reticulocytes, total bilirubin, and any additional safety testing done on the neonate on an ad hoc basis.

RLYB212 immunogenicity data and the presence of ADA, and whether there is a neutralizing response, will be determined.

Pregnancy and neonatal outcomes following antenatal RLYB212 administration will include:

- Number of spontaneous abortions, defined as non-deliberate fetal death which occurs prior to GW 19.
- Number of elective abortions, defined as deliberate termination of pregnancy at any time in gestation.
- Number of stillbirths, defined as non-deliberate fetal death anytime in gestation on or after GW 19.
- Number of premature births, defined as live birth prior to GW 37.
- Number of full term births (\geq GW 37).
- Overall health and development of infants at 4-6 weeks and 12 months of age.

- Neonatal thrombocytopenia and severe neonatal thrombocytopenia, as defined by a platelet count $< 150 \times 10^9/L$ and $< 50 \times 10^9/L$, respectively, collected as a part of the cord blood sample.

Maternal alloimmunization to HPA-1a will be determined by a measurement of maternal circulating anti-HPA antibodies at 10 weeks postpartum or 10 weeks from the date of the pregnancy-terminating event (ie, abortion [spontaneous/elective] or stillbirth).

Where possible, data will be summarized using descriptive statistics and listed.

9.4.4 *Tertiary/Exploratory Endpoints*

Not applicable.

9.4.5 *Other Safety Analyses*

All routine safety analyses will be performed on the Safety Analysis Set. Data will be presented separately for maternal participants and neonates/infants.

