4.3. Secondary Endpoint Analysis

4.3.1. RLYB212 Exposure in the Neonate at Delivery

4.3.1.1. Concentration of RLYB212 in Cord Blood

A cord blood sample will be collected at parturition to assess neonate exposure to RLYB212. Neonate serum concentration will be listed only for all newborns for the RLYB212 PK analysis set. Serum concentrations below BLQ will be imputed as 0.

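### The cord serum RLYB212 level leaves out drug bound to fetal cells, so a low or unquantifiable value in an HPA-1a positive neonate cannot be read as low fetal exposure

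*Protocol*

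**What the plan says.** The secondary objective on neonatal exposure at delivery has one endpoint, "Concentration of RLYB212 in cord blood" (Protocol 1.1 and 3.1). Protocol 9.4.3 adds: "RLYB212 exposure in the neonate will be evaluated by cord blood concentration of RLYB212, which will be a single measurement". Protocol 8.2 gives the purpose: "A cord blood sample will be collected at parturition to inform neonate exposure to RLYB212". Table 2-1 lists the sample among the mitigations for fetal risk: "A cord blood sample will be collected at delivery to evaluate fetal exposure to RLYB212".

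SAP 4.3.1.1 repeats the purpose ("A cord blood sample will be collected at parturition to assess neonate exposure to RLYB212"), describes the result as a neonate serum concentration, plans a listing only, and sets values below quantification to 0.

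The Screening Part 1 criteria (Protocol 5.1.1) require an HPA-1a/b fetus. A first dose may be given while the fetal genotype is pending, but treatment stops if the fetus proves to be HPA-1b/b (Protocol 8.1.2).

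Two statements in Protocol 2.2.2.1, Nonclinical Studies, bear on this endpoint. For the toxicity study in heterozygous antigen-positive mice: "the assay used to measure RLYB212 in circulation detects only free drug, which limits the ability to accurately assess exposure levels in antigen positive animals". A parallel antigen-negative arm was added there to estimate exposure. For the reproductive studies: "While direct measurement of RLYB212 exposure in heterozygous antigen positive offspring was not possible". Exposure margins in antigen-positive offspring were extrapolated from antigen-negative controls.

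**The concern.** The human neonates have the same antigen status as the mouse offspring that the sponsor could not measure directly. In mice the sponsor added controls and extrapolated. In the trial nothing comparable is planned: no stated assay format, no control, no interpretation rule and no caveat.

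At stake is what a low cord value may be taken to mean. It fits two opposite states: little drug crossed the placenta, or drug crossed and is bound to fetal antigen. The second is the one that matters for fetal safety, and it would look reassuring. The DMC receives exposure data together with neonatal safety data at its cohort reviews (Protocol 4.1, SAP 4.6), so the ambiguity reaches the people who judge fetal risk.

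**Working it through.** No sample size, power or alpha figure is involved, and the plan gives no figure for this bias. The check is a reading of the documents, followed by an illustration of size.

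**1. Does the clinical assay read free or total drug?** Not stated. Protocol Appendix 2 says only that RLYB212-specific tests are run in central laboratories. The free-drug sentence describes the assay of the mouse study.

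**2. Does the answer remove the problem?** No.
- The SAP matrix is serum, which contains no platelets or tissue.
- The target is integrin β3. Protocol 2.2.2.1 reports staining of platelets and placental trophoblasts in the adult tissue panel, and of endothelial and various epithelial cells in fetal tissue.
- Protocol 4.3 anticipates target-mediated loss through HPA-1a on placental proteins, and Table 2-1 lists placental binding as a fetal risk.
- Drug held on cells is outside the sample under either format. A total-drug assay would add back only drug bound to antigen that is itself in the serum.

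**3. What happens to a value below LLOQ?** SAP 4.3.1.1 turns it into 0. The documents give no numerical LLOQ, so how often this would occur cannot be computed.

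**4. Illustration of size.**
- From the documents: 10 ng/mL is 0.067 nM (Protocol 9.2). At an assumed 150 kDa this reproduces: 10 / 150 = 0.0667 nM. On the same basis 3 ng/mL is 0.020 nM.
- Assumption: ~3 ng/mL is the free level that gives the ~10% occupancy cited for the lower target bound. Then Kd = 0.020 × 0.9 / 0.1 = 0.18 nM. The protocol says only that the bound is supported by such data.
- Assumption: R, the accessible fetal HPA-1a concentration, is not in the documents and is varied from 0.02 to 10 nM.
- With total drug T and 1:1 binding, bound C = ½[(T + R + Kd) − √((T + R + Kd)² − 4TR)], and unbound F = T − C.
- Example, T = 0.0667 and R = 1: the sum is 1.2467, the root is 1.1347, C = 0.0560, F = 0.0107 nM, which is 1.6 ng/mL.

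| Assumed R (nM) | Unbound drug when total is 10 ng/mL | Share of total |
|---|---|---|
| 0.02 | 9.2 ng/mL | 92% |
| 0.1 | 6.9 ng/mL | 69% |
| 0.5 | 2.8 ng/mL | 28% |
| 1 | 1.6 ng/mL | 16% |
| 5 | 0.35 ng/mL | 3.5% |
| 10 | 0.18 ng/mL | 1.8% |

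The shortfall runs from negligible to 10 / 0.18, about 56-fold. A cord reading of 1.6 ng/mL could come from a total of 1.6 ng/mL with no binding, or from 10 ng/mL with R = 1 nM. The single value cannot tell these apart.

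**The case against.** Several points on the other side stand.

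- A reader might infer that the protocol declares its clinical assay to be free-drug only. It does not; that sentence belongs to a mouse study, where it says accuracy was limited. The stronger statement, that direct measurement was not possible, concerns mouse offspring only.
- A reader might infer that cord values will be falsely low. A serum reading may be a correct circulating concentration. What it can understate is circulating plus cell-bound drug.
- A reader might take one point of the table as the size of the bias. The antigen concentration is assumed and Kd rests on a simplified reading of the ~10% figure, so no single size is supported.
- A reader might infer that dosing of the next cohort turns on the cord level. Table 2-1 names maternal PK at the end of pregnancy as what is evaluated first, dose changes rest on PK from completed pregnancies (Protocol 6.5), and no cord threshold is set.
- The same cord sample yields platelets, hematocrit, hemoglobin, reticulocytes and bilirubin, so the consequences of heavy platelet binding are looked for directly. Severe fetal or neonatal thrombocytopenia or hemorrhage triggers a hold for all participants (Protocol 7.1.2).
- Table 2-1 offers the cord level as one of several mitigations, and the SAP only lists it.

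It might also be said that a total-drug assay would settle the matter. That does not stand, because cell-bound drug is not in serum. Nor do the platelet count and the hold rule repair the exposure endpoint: they measure consequence, and neither document says how a low concentration should be read.

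**Conclusion.** The point holds as a limit on interpretation that the plan does not state. The endpoint measures circulating RLYB212 in cord serum, and both documents present it as exposure of the fetus or neonate. In HPA-1a positive neonates it can understate total fetal exposure. It cannot support a conclusion that exposure was low, and the rule that sets unquantifiable values to 0 displays the ambiguous case as none.

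Confidence is high that the safeguard is missing. The direction (circulating drug at or below circulating plus bound) follows from the matrix and from where the antigen sits, and assumes that the cord sample is assayed as serum, as the SAP says. The size is not known from the documents: negligible to more than 50-fold under the assumptions shown.

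Practical reach is now small. SAP 4.9 records early termination with one participant enrolled and listings only, and its enumeration of listings does not name drug concentrations. Any cord value that is reported still needs the caveat.

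**What to change.** - In Protocol 3.1, 8.2, 9.4.3 and Table 2-1, and in SAP 4.3.1.1, label the endpoint as circulating (not cell-bound) RLYB212 in cord serum, and state whether the assay reads free or total drug.
- In the same places, state that a low or unquantifiable value in an HPA-1a/b neonate is not evidence of low fetal exposure.
- In SAP 4.3.1.1, report <LLOQ, with the LLOQ given, in place of 0.
- For the DMC and the report, list each cord value beside the maternal Visit 14 concentration and the cord platelet count. Both are already collected (Protocol Table 1-3).
- An estimate from the maternal level times a fetal:maternal ratio is optional and should not replace the measurement. The only ratio in the documents is ~1-3 fold, from antigen-negative control mice at gestation day 18 (Protocol 2.2.2.1). Any such estimate must be shown as a range and labelled as extrapolated from those animals.

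Cost: wording, one changed listing rule and two added columns, with no new samples. The price is a weaker claim about neonatal exposure.
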